1. SUMMARY

Rationale: Lack of postoperative acute pain management is associated with increased morbidity, longer recovery time, more opioid use and subsequently increased health care costs. There is increasing evidence virtual reality (VR) is effective in the reduction of acute pain. Alternative methods to reduce postoperative pain and multimodal analgesia are necessary for acute postoperative pain management and to reduce opioid use and their adverse effects.

Objective: The aim of this study is to explore the effect of VR on pain in the immediate postoperative period after elective gynecological surgery.

Secondary objectives are evaluating pre-and postoperative anxiety, pain catastrophizing, analgesic use, length of hospital stay between both groups and to explore tolerability, feasibility and satisfaction of VR use.

Study design: The study concerns a non-blinded, single centre, randomised controlled trial.

Study population: Eligible women fulfill the inclusion criteria and receive elective gynecological surgery under spinal anesthesia in the Zuyderland Medical Centre location Heerlen.

Intervention: The study population will be randomly divided into the intervention group (VR-group) or the standard care- group. The intervention group can choose for an immersive guided relaxation VR experience or an interactive VR experience during the pre- and postoperative period additional to the usual standard care. The participants randomised to the standard care- group will receive only the usual standard care pre-and postoperative.

Main study parameters: The primary outcome is postoperative pain measured on a numeric rating scale (NRS). A total of 30 patients have to be included in each group. This means that a total of 60 women will have to be included in the study.

Nature and extent of the burden and risks associated with participation, benefit and group relatedness:

The study population experiences a small medical risk when participating to this study. They can experience side-effects of VR for example dizziness or nausea and in rare cases epileptic insults.

Participants of the study have to fill in a questionnaire before randomization and pre-and postoperative score of pain and anxiety on a zero to ten score scale.

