4. STUDY DESIGN

The design of this study is a single centre, randomised controlled trial (RCT). Eligible patients will be randomised to either the VR- group and receive additional VR during the pre- and postoperative period or undergo standard pre- and postoperative management (standard care- group).

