6. TREATMENT OF SUBJECTS

6.1 Investigational product/treatment

The study population will be randomly divided into the intervention group (VR-group) or the standard care-group.

Intervention group (VR-group):

The participants randomised into this group can choose for an immersive guided relaxation VR experience or an interactive VR experience. We will register which option the patients choose. The options are explained in paragraph 9.3. Pre-operatively when arriving at the pre-operative anesthetic room, the level of anxiety and pain is scored using the numeric rating scale (NRS) (T1a). After this, the VR- group will receive their VR experience of own choice on the pre-operative anesthetic room during 10-15 minutes. Directly after this VR intervention, the level of anxiety and pain is scored from 0-10 (T1b).

Direct postoperatively after arriving on the recovery ward, NRS score and level of anxiety from 0-10 will be scored by the participant (T2). Subsequently, the VR-group will receive the VR experience of own choice during 10 minutes. Before leaving the recovery ward, NRS score and level of anxiety from 0-10 will be measured (T3). Depending on the duration of stay on the recovery ward, an extra VR intervention will be given. If the patient stays for less than 3 hours, there will only be one VR intervention. If this is longer than 3 hours, there will be two interventions. The VR intervention is additional to the standard postoperative care management, the standard pain protocol is explained below.

The VR-intervention will be given using the Oculus Go Virtual Reality glasses with touchpad.

Standard pre-and postoperative management (standard care- group):

The participants randomized into the standard care- group will receive the usual standard pre-and postoperative management. Pre-operatively when arriving at the pre-operative anesthetic room, the level of anxiety and pain is scored from 0-10 (T1a). After 10-15 minutes the level of pain and anxiety is again scored from a scale from 0-10 (T1b). Direct postoperatively after arriving on the recovery ward, measurements like NRS score and level of anxiety from 0-10 will be scored by the participant (T2). Before leaving the recovery ward, NRS score and level of anxiety from 0-10 will be measured (T3).

Standard pain protocol:

1. Preoperative (arrival day-care unit) start with 1000mg paracetamol orally administered.

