Attachment 5. VR-questionnaire

We would like to ask you some questions about your experience with Virtual Reality (VR).

1. How did you experience the use of VR before surgery?

- Very pleasant
- Pleasant
- Neutral
- Unpleasant
- Very unpleasant

2. How did you experience the use of VR after your surgery?

- Very pleasant
- Pleasant
- Neutral
- Unpleasant
- Very unpleasant

3. Did the VR-experience contribute in reducing your pain experience before your surgery?

- Very likely
- Likely
- Pretty likely
- Not likely
- Not likely at all

4. Did the VR-experience contribute in reducing your pain experience after your surgery?

- Very likely
- Likely
- Pretty likely
- Not likely
- Not likely at all

5. Did the VR-experience reduce your anxiety level before surgery?

- Very likely
- Likely
- Pretty likely
- Not likely
- Not likely at all

6. Did the VR-experience reduce your anxiety level after the surgery?

- Very likely
- Likely
- Pretty likely
- Not likely
- Not likely at all

7. Would you choose the use of VR during a surgery under spinal anesthesia the next time you will have to get surgery?

- Very likely
- Likely
- Pretty likely
- Not likely
- Not likely at all

8. The use of the VR-app is easy:

- Completely agree

- Agree
- Neutral
- Disagree
- Completely disagree

9. Would you recommend the use of VR during a surgery under spinal anesthesia to your friends, family or others?

- Very likely
- Likely
- Pretty likely
- Not likely
- Not likely at all

10. How easy was the use of VR before or after surgery?

- Very easy
- Easy
- Pretty easy
- Not that easy
- Not easy at all

11. How visually attractive was the VR-experience before and after surgery

- Very attractive
- Attractive
- Pretty attractive
- Not that attractive
- Not attractive at all

12. Did you prefer anything else in the VR-app?

- No
- Yes, if yes circle what you prefer,

A more active game component
A less active game component
Only relaxing images

13. Did you experience any side-effects during the use of the VR-app?

- No
- Yes, if yes circle the side-effects;

Nausea
Dizziness
Other:

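### VR-questionnaire items 7 and 9 place VR during the operation, although the trial gives it only before and after, so the two acceptance answers are ambiguous

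*Combined protocol and SAP*

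**What the plan says.** Every description of delivery puts VR on one side of the operation or the other. Section 4 says the intervention group will "receive additional VR during the pre- and postoperative period", and the Summary describes the "interactive VR experience during the pre- and postoperative period additional to the usual standard care".

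Section 6.1 gives the detail:
- Before surgery, the VR group "will receive their VR experience of own choice on the pre-operative anesthetic room during 10-15 minutes".
- After surgery, once the T2 scores have been taken on the recovery ward: "Subsequently, the VR-group will receive the VR experience of own choice during 10 minutes".
- A possible further session is also tied to the recovery ward: "Depending on the duration of stay on the recovery ward, an extra VR intervention will be given".

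Two items of the VR-questionnaire in Attachment 5 are framed differently. Item 7 asks "Would you choose the use of VR during a surgery under spinal anesthesia the next time you will have to get surgery". Item 9 asks "Would you recommend the use of VR during a surgery under spinal anesthesia to your friends, family or others". Other items in the same form use before and after, for example item 10: "How easy was the use of VR before or after surgery".

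The form supplies a listed secondary outcome, the tolerability, feasibility and satisfaction of VR use (sections 3 and 9.1.2). Section 9.3 says it is given on the ward after surgery to evaluate the VR experience. Section 11.2 summarises it as means and frequencies and defines nothing at item level.

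**The concern.** Whether a patient would choose VR again, and whether she would recommend it, are natural headline results for satisfaction. Both questions, as printed, attach VR to a period in which the trial does not use it.

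A woman who liked her two sessions but would not want a headset on during the operation could answer unfavourably. A woman who would welcome distraction in theatre could answer favourably whatever she thought of the sessions she had. The distortion could therefore go either way, and a table of frequencies would not show it.

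What is at stake is the meaning of two reported percentages or means. No treatment comparison depends on them.

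**Working it through.** The plan gives no figure to reproduce here. The check sets the delivery schedule beside the item wording.

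**1. When VR is given.**

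| Place in the protocol | Timing of VR |
|---|---|
| Summary; section 4 | Pre- and postoperative period |
| Section 6.1, before surgery | Anesthetic room, 10-15 minutes, between T1a and T1b |
| Section 6.1, after surgery | Recovery ward, 10 minutes, after T2 |
| Section 6.1, extra session | Recovery ward, if the stay is longer than 3 hours |
| Section 9.3, study schedule | T0 ward, T1 anesthetic room, T2 and T3 recovery ward; no time point in theatre |

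Intraoperative VR sessions described anywhere: 0.

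**2. What the 13 items refer to.**

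| Items | Timing named in the item | Count |
|---|---|---|
| 1-6, 10, 11 | Before and/or after surgery | 8 |
| 7, 9 | During a surgery | 2 |
| 8, 12, 13 | None (ease of the app, content preference, side-effects) | 3 |

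8 + 2 + 3 = 13. Items 7 and 9 are the only two on choosing VR again or recommending it, so no other item can stand in for them.

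**3. What the ambiguity does to a reported frequency.** Assume that respondents who read the phrase as the whole surgical episode answer about the VR they received. Let *w* be the share who instead read it literally. Among those literal readers, let *p_I* be the proportion favourable to VR in theatre, and *p_D* the proportion who would have been favourable if asked about the sessions they had. Then

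error in the reported proportion = *w* × (*p_I* − *p_D*).

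- If *w* = 0, the error is 0.
- If *w* = 1, the error is the full difference *p_I* − *p_D*.
- The sign depends on which of *p_I* and *p_D* is larger.

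The form collects nothing that estimates *w* or *p_I*. Items 1 and 2 rate how pleasant each session was. That is related to *p_D*, but it is not the same question as choosing VR again or recommending it. The error therefore cannot be estimated or corrected from the completed forms.

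**The case against.** The best defence is context. The form opens by asking about the patient's own experience with VR. She reaches item 7 after six items on VR before and after her operation, and item 7 asks about next time, which suggests repeating what she had. Read that way, the phrase means the surgical episode as a whole and the answer is on target.

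In addition, inclusion requires native Dutch speakers (section 5.2), so patients may well complete a Dutch form whose preposition is different. The documents neither confirm this nor include a Dutch text.

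This defence stands in part. A reader might infer that items 7 and 9 simply rate a different, intraoperative intervention. The documents do not support that, because the loose reading is plausible. They do not exclude the literal reading either. Six items that distinguish before from after give a respondent reason to take 'during' as a third period, and under spinal anesthesia a headset in theatre is imaginable. The defence turns the fault into ambiguity but does not remove it.

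A reader might also infer that the sponsor will present these answers as acceptance of perioperative VR. Section 11.2 makes no such claim. It plans means and frequencies, and specifies no composite score, test or decision rule for this outcome.

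Finally, a reader might extend the criticism to items 10 and 11, which each take one answer for both sessions. That is a matter of preference. Items 1-6 already separate the sessions for pleasantness, pain and anxiety, and a single overall rating of ease or visual attractiveness is legitimate. At most, ease of use cannot be split by session. It does not follow that postoperative feasibility as a whole cannot be assessed.

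**Conclusion.** The mismatch between items 7 and 9 and the delivery schedule is real and can be seen on the face of the documents. If the form is used as printed, the answers may mix two meanings, and the two frequencies cannot be cleanly interpreted as acceptance of the VR delivered.

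The size is minor: 2 of 13 items, though both of the items on future choice and recommendation, in one of seven listed secondary outcomes, and a descriptive one. That none of the 30 planned VR patients is scheduled for VR in theatre restates the mismatch and does not measure its impact. The primary pain outcome, items 1-6 and the remaining secondary outcomes are unaffected.

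The conclusion assumes that patients see wording equivalent to the English attachment. If a Dutch version already refers to VR before and after surgery, only the attachment needs aligning.

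**What to change.** Reword items 7 and 9 so that both ask about the use of VR before and after a surgery under spinal anesthesia, in line with the timing words used elsewhere in the form. Check that any Dutch version given to patients says the same, and correct whichever text is out of step.

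If some forms have already been completed, report those answers separately from answers to the reworded items. Give the exact wording used, and do not describe them as acceptance of the VR delivered. This avoids misstatement but does not recover the intended answers.

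The cost is two edited lines on a form about VR use, with notification as an amendment under section 13.3 if the favourable opinion has already been given. Sample size, visits, randomisation and analysis do not change. Splitting items 10 and 11 by session is optional and not part of this correction.
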